10.13 PROTECTION OF SUBJECTS

Potential subjects will be screened for conditions that would preclude use of PGB, LFX or XR-NTX. Adverse events will be monitored by medical and research staff on a daily basis. Subjects will be given a 24-hour emergency number they can call if necessary. If the subject is discontinued from study treatment due to, an AE, he/she will be followed by medical staff until it resolves or becomes stable. Potential subjects will be excluded if they have a history of a severe psychiatric disorder (schizophrenia, bipolar I, depression with suicidal attempts); impairment of renal function; severe liver disease; participated in a medication study within the last 30 days; have an illness which may require hospitalization during the study; history of allergy or other SAE due to treatment with PGB, XR-NTX or LFX, taking sympathomimetic drugs, or a thiazolidinedione antidiabetic; or impending incarceration;. Pregnant females or women who refuse to use acceptable forms of birth control will also be excluded.

10.13.1 Venipuncture. Venipuncture will be carried out with good aseptic technique by a nurse or physician or qualified designated person.

10.13.2 Risks Associated with Study Procedures

- Behavioral Ratings: Risks are minimal and limited to breach of confidentiality or becoming anxious or embarrassed by some of the questions. Procedures to protect confidentiality and reduce study-related anxieties are described in section 22.0.
- Potential Benefits: Subjects benefit from close medical and psychiatric attention over and above that which they receive in an inpatient detoxification.

10.13.3 Risk Benefit Ratio: The first step for transitioning from opioid addiction to antagonist treatment is detoxification, often using an alpha-adrenergic agonist such as clonidine or LFX. However, patients often drop out due to the dysphoria and other uncomfortable subjective effects of withdrawal and do not transition to naltrexone. The recent studies summarized above provide data to suggest that PGB can reduce these subjective effects, however the risks and benefits of a /LFX combination have not been studied. Both medications are FDA-approved and we have no reason to think they cannot be safely used together, but they have not been tested.

Identifying a dosing combination that improves detoxification success and transition to antagonist treatment has the potential to improve the number of patients that benefit from its relapse and overdose protection effects. For these reasons, we think that the risk/benefit potential of this dosing combination is significant in the likely event that it is safe and effective.

10.13.4 Medical Management of Adverse events. Evaluation and management of AE's may include additional medication, transfer to a medical unit, reduction in study of medication, temporary cessation of study drug, or early termination from the trial if necessary.

11.0 METHODS FOR ASSIGNING SUBJECTS TO TREATMENT GROUPS

11.1 RANDOMIZATION

[name] will develop a program using computer-generated, randomly permuted blocks within each site

that are stratified according to male/female. Upon completing screening assessments, research staff will request randomization be performed by the site research pharmacy. The patient will be sequentially assigned to the next treatment based on male/female status. At all sites, patient treatment will correspond to a unique randomization number.

Penn IDS will upload the randomization lists into a Treatment Unmasking Program, per IDS SOP-309. Access to this trial within the program will be provided to authorized Penn users. In the event of an emergency, unmasking can occur at any time using the subject's assigned randomization number. The user will not be unmasked to the treatment of other subjects. For other sites, [name] will give the randomization list to PENN IDS who will be responsible for maintaining the randomization blind.

11.2 RANDOMIZATION OF PLACEBO AGENT

The Penn IDS will prepare the placebo medication as matching blinded capsules containing Lactose Monohydrate, Spray-Dried, NF. Blinded placebo capsules will be packaged into blister packs along with lofexidine tablets, in separate compartments that are labeled for dosing times on days 1-7 and ship them to the research sites.

11.3 BLINDING OF STUDY DRUG

Penn IDS will prepare blinded PGB capsules by over-encapsulation of the drug into shells matching the placebo capsules. Blinded PGB capsules will be packaged into blister packs along with LFX tablets, in separate compartments that are labeled for dosing times on days 1-7 and ship them to the research sites.

11.4 RECEIPT OF XR-NTX

The study will use XR-NTX in 380 mg kits supplied by Alkermes, Inc. Alkermes will ship directly to each site a shipment of 20 XR-NTX kits per site. Sites will be responsible for receiving, storage, administration, and accountability for each subject. Sites must use the DIMS system for accountability of dispensed Vivitrol to control product expiration dates. Sites will also be responsible for the destruction and expiration of unused drug (see destruction procedures for XR-NTX). Accountability, expiration, and destruction will be recorded on a XR-NTX accountability log. Each site will administer XR-NTX according to the package insert instructions.

11.5 RECEIPT OF NALOXONE

Subjects will be offered a naloxone challenge on day 8 using 0.8 mg or 1.0 mg I.M. If the COWS scores do not rise above 10 within 15-30 minutes, subjects will receive an injection of XR-NTX* given by a study nurse (or NP, etc.), physician (or PA, etc.) or other licensed and trained health care provider. Each site will acquire their own supply of naloxone and will be responsible for the storage, accountability, and dispensing throughout the trial. (*Naloxone challenge and receipt of XR-NTX is optional. Subject can request guidance on another form of treatment).

11.6 PREPARATION AND ADMINISTRATION OF STUDY DRUG

Study medication will be prepared by the Investigational Drug Service at the Hospital of the University of Pennsylvania ([contact]). It will be sent to the sites and stored and dispensed by their respective research pharmacies/or designated unit at the three sites.

11.7 COMFORT MEDICATIONS

In addition to study medications, subjects can receive, as needed, the following "comfort" medications: ondansetron 4 mg or 8 mg tidPO PRN for nausea and vomiting, trazodone 100 mg HS PRN insomnia, loperamide 2 mg qid PO PRN diarrhea, and a non-steroidal such as Ibuprofen 600 mg qid PO PRN for aches and pains or acetaminophen 650 mg (2 tablets 325 mg) PO qid PO PRN, cyclobenzaprine 5 mg tid PO PRN for muscle aches and pains, and hydroxyzine 25 mg qid PO PRN anxiety. In cases of QTc prolongation that are not >550ms or judged to require stopping study medications, diphenhydramine 50 mg hs PO PRN may be used for insomnia, and trimethobenzamide 300 mg qid PO PRN for nausea. It is permissible to give comfort medication at visit 8 for Day 8, 9, and at Day 10 for visit 10, 11, 12, 13, 14 and 15. No comfort medication will be given by the study after Day 15. Comfort medications on Day 15 are counted up to and including what was taken at the time of visit on calendar day 15. Comfort medication needed after Day 15 will be considered non-study follow-up care. Patients can get comfort medications even if they don't opt for XR-NTX).

Each site will maintain records on use of these medications on the Comfort Medication Log. Comfort medications will be acquired, stored, and dispensed by each site's research pharmacy or designated person. Store according to the information found in the package insert.

11.8 PRIOR AND CONCOMITANT MEDICATIONS

Prior and concomitant medications are defined as any medications taken before enrolling in the study that continues into the study and any medication (not comfort medication or study drugs) that are prescribed during the study. They are not the study medications (those provided in the blister packs). They must be recorded on the study concomitant medication form and entered into the database. For example, a diuretic for hypertension medication. All field (start date, dose, times per day, stop date, etc.) must be captured and recorded for the month before the initial screening visit through the follow up assessment.

11.9 RULING OUT CURRENT PHYSIOLOGIC DEPENDENCE BEFORE XR-NTX ADMINISTRATION (NALOXONE CHALLENGE)

The COWS will be performed before administering XR-NTX, to assess the subject's signs/symptoms of withdrawal. Naloxone administration should start with a split dose of 0.2 mg first, wait 10-20 minutes, then 0.6 mg (0.8 mg total). Following in the challenge, the patient should be monitored for 15-30 minutes for the appearance of opioid withdrawal. The absence of physiologic opioid dependence is seen by COWS scores that are < /=10. If clinically significant withdrawal is shown, a study physician will treat it with one or more of the approved non-narcotic "comfort" medications.

- 1. Signs and Symptoms of a positive naloxone challenge might include:
 - Objective—tearing, sweating, goose bumps, shakes, vomiting, pupillary dilatation, vital sign increases

11/2/2022

- Subjective—feeling of temperature change, joint and/or muscle pain, bone pain, nausea, abdominal cramping, skin crawling
- 2. If opioid abstinence syndrome is precipitated by naloxone, symptoms will be apparent within a few

Protocol V9.0

minutes and maximal within 20 minutes after administration, but the patient must be observed for 15-30 minutes

If manifestations of opioid withdrawal are evident following the naloxone challenge do not initiate naltrexone therapy due to potential risk of precipitating more severe and prolonged withdrawal with XR-NTX; the naloxone challenge test may be repeated in 24 hours (inpatient Day 9) in these patients.

If withdrawal symptoms are present, the patient should be treated with withdrawal reducing medication or equivalent and observed until symptoms have resolved (about 20 minutes).

If evidence of withdrawal is absent, naltrexone therapy may be initiated. Please note that even minor and/or transient GI symptoms following naloxone challenge be considered evidence of withdrawal since patients with such symptoms will often develop severe and disturbing GI symptoms if XR-NTX therapy is then initiated.

- 3. Signs and Symptoms of positive naloxone Challenge might include:
- Objective—tearing, sweating, goose bumps, shakes, vomiting, pupillary dilatation, vital sign increases
- Subjective—feeling of temperature change, joint and/or muscle pain, bone pain, nausea, abdominal cramping, skin crawling
- 4. If an opioid abstinence syndrome is precipitated by naloxone, symptoms will be apparent within a few minutes and maximal within 20 minutes after administration.

If manifestations of clinically significant opioid withdrawal are evident following the naloxone challenge test, do not initiate naltrexone therapy due to potential risk of precipitating more severe and prolonged withdrawal with naltrexone; naloxone challenge test may be repeated in 24 hours (inpatient Day 9) in these patients.

If withdrawal symptoms are present, the patient should be treated with the clinically most appropriate withdrawal reducing medication and observed until symptoms have resolved (about 20 minutes).

If evidence of withdrawal is absent, naltrexone therapy may be initiated. Please note that even minor and/or transient GI symptoms following naloxone challenge be considered evidence of withdrawal since patients with such symptoms will often develop severe and disturbing GI symptoms if XR-NTX therapy is then initiated.

12.0 RECEIVING, STORAGE, DISPENSING AND RETURN

12.1 RECEIPT OF PGB, LFX, AND XR-NTX

PGB and LFX will be prepared in blister packs and shipped to the research pharmacies or designated persons at each treatment site by the Investigational Drug Service at the University of Pennsylvania. Resupply of packs is requested by email to: [contact]. Upon receipt of study treatment medication, an inventory is to be completed and a drug receipt log filled out and signed by the person accepting the shipment. It is important that the designated study staff count and verify that the shipment contains all items noted in the shipment inventory. Any damaged or unusable study drug in a shipment (active drug or comparator) will be documented in the study files. XR-NTX will be shipped by Alkermes directly to the sites. The sites are responsible for destruction of the study medication per the site's documented procedures and regulations for controlled substances.

12.2 STORAGE OF INVESTIGATIONAL MEDICATION

Study medication will be sent from the Penn Research Pharmacy to the sites and stored at their research

pharmacies or designated research medication storage sites. It must be stored at 20°C to 25°C (68°F to 77°F) with excursions permitted to 15°C - 30°C (59°F to 86°F). Each site should maintain temperature records throughout the trial and be able to provide them upon request. If sites have a temperature excursion relating to study drugs, please contact the Investigational Drug Service at [contact].

12.3 DISPENSING OF INVESTIGATIONAL MEDICATION

After randomization, study drug will be dispensed to each subject from an assigned blister pack according to his/her randomization number at the appropriate times by nurses on the inpatient units at the collaborating site. Unused study medication will be collected per site SOP.

12.4 RETURN AND DESTRUCTION OF STUDY DRUG

All unused study medication is to be saved, documented, and returned to the Research Pharmacy or designated person at each site and destroyed at the site according to SOPs for that site. Upon completion of the study, there will be a final reconciliation of study medication that was provided, consumed, and returned. Penn IDS will maintain inventory and subject accountability in Vestigo, an electronic, web-based pharmacy research program. A similar inventory reconciliation will be performed at each site. If electronic recording is not used at the collaborating sites, the research pharmacy or designated person(s) at the site will keep records for the reconciliation of administered, spoiled, expired, and unused drug. Paper logs must be signed and dated and any discrepancies noted will be investigated, resolved, and documented. Unused study drug will be destroyed in a manner consistent with regulations governing Schedule V medications. Medication should not be destroyed until the QA monitor has audited the drug accountability log.

12.5 DISPENSING XR-NTX

On day 8 or 9, a 380 mg injection of XR-NTX will be administered according to subjects' consent and evidence that detoxification has been successful, by a negative naloxone challenge. Dosing will be maintained in a Drug Accountability Log and recorded in RedCap. Subjects who are unable to find an outpatient provider will be offered a second dose of XR-NTX up to 5 weeks after day 8 or 9 (day 36 ± 7 days).

12.6 STUDY DRUG ACCOUNTABILITY

US WorldMeds LLC will provide LFX and send it to the University of Pennsylvania's IDS pharmacy. Penn IDS will acquire PGB for all sites and the supplies necessary for preparing active and placebo blister-packs. Alkermes, INC. will provide XR-NTX and will send it to each collaborating site. Comfort medications and naloxone will be acquired separately by each site.

All study drug received, dispensed, administered, and returned will be managed by study site personnel and site pharmacies for sites, and the Penn Investigational Drug Service for the PENN site. Medications must be used only as described in the protocol and by the appropriately licensed Investigators named in Form FDA 1572. Study staff will retain the original individual blister-cards, including those empty, partially empty, or full, as well as used and unused XR-NTX kits. Unused medications will be collected and handled as per site SOP. Disposition of any study drug lost or damaged must be documented on the site accountability log or by a report by the site pharmacy. Unused or expired study drug will be retained at the participating site or pharmacies until the site is monitored. After the monitor audit, unused medication can be destroyed according to their usual procedures and documented in the regulatory file.

13.0 STATISTICAL PLAN

13.1 DATA ANALYSES

[name], the CSA Statistician, and his staff will perform data analyses. Prior to analyses, standard data screening/cleaning procedures will be applied. These procedures will screen the data for data-entry errors, check for outliers, assess the extent and pattern of missing data, and check that appropriate assumptions of normality are met whenever necessary.

13.2 **SAMPLE SIZE DETERMINATION**

Power Analyses: The primary goal of this study is to determine if the PBG/LFX combination versus LFX/PGB-PLA is safe and effective in OUD individuals, and shows a reduction in opioid–related withdrawal effects greater than lofexidine alone. To assist in this determination, we provide power for the primary comparison of longitudinal subjective withdrawal measures, comparing the groups on rate of decrease across days, using a linear group by time effect for the mixed effects models described above. We have one primary outcome, so use an alpha level of 0.05, and we use two- sided tests. 90 subjects, approximately 30 from each of three sites (MMTC and PENN might have more than 30), who will be randomized into two groups, with 30 assigned to LFX/PGB-PLA, and 60 to LFX plus a starting daily dose of 400 mg of PGB and increasing to 600mg PGB on day 2. Assuming an overall dropout rate of 40%, and within-subjects' correlations of 0.5, the methods of Hedeker et al (Hedeker, Gibbons and Waternaux, 1999) show that this provides 80% power for a group by linear time interaction effect of Cohen's d=0.44 standard deviations between the two groups.

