
Outpatient screening is used to determine eligibility for the study. It will consist of the 30 days prior to inpatient admission for study detoxification and treatment. On day 1 of inpatient treatment subjects will be randomized to PGB/LFX or PGB-PLA/LFX for a 7-day detoxification. On day 8, if the patient completes **Duration of subject** detoxification, continues to be interested in XR-NTX treatment, provides a urine, participation and and passes a naloxone challenge, he/she will be offered one injection of XR-NTX before hospital discharge. This injection of XR-NTX is optional. If retests must be medication administration done, such as a repeat of the naloxone challenge, all subjects are eligible to remain inpatient until Day 9. All subjects, whether they receive XR-NTX or not. will be referred to continuing care and asked to return to the research outpatient clinic on days 10 and 15 for follow-up visits. Subjects who cannot find a provider may be offered an additional XR-NTX injection up to 5 weeks after the Day 8 injection. Reference therapy PGB-Placebo plus lofexidine The primary outcome is reduction in subjective withdrawal as measured twice/day using the Short Opiate Withdrawal Scale (SOWS- Gossop). SOWS scores range from zero to 30. Groups will be compared on 10 or more repeated SOWS responses during inpatient treatment using linear mixed-effects regression models. The SOWS total will be regressed on a three-level factor for site, and a two-level factor for pregabalin dose, with random intercept and correlated residuals and a random slope included if necessary for fit. Contrasts Statistical between the combined groups will be estimated from this model. Methodology The secondary outcome is an ordinal response indicating completion of detox and receipt of antagonist treatment, with levels (1) failure to complete detox, (2) completion of detox with failure to receive antagonist treatment, and (3) completion of detox and receipt of antagonist treatment.

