9.2 PRIMARY OUTCOME ENDPOINT

Reduction in subjective withdrawal as measured by the SOWS-Gossop.

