13.3 STATISTICAL METHODS

13.3.1 Primary Outcome - Reduction in SOWS-Gossop criterion. The primary outcome will be reduction in subjective withdrawal as measured by the SOWS - Gossop (scores range from zero to 30). The groups will be compared on the 14 repeated SOWS-Gossop responses obtained during the seven-day detoxification period, using linear mixed-effects regression models; the SOWS-Gossop total will be regressed on a three-level factor for site, and a two-level factor for medication group, with time and group by time effects. The covariance structure will include a random intercept and correlated residuals, with a random slope included if necessary for fit. Contrasts between the PGB group and the PGB-PLA group will be estimated from the model. Exploratory analyses of heterogeneity of dose effects across sites will be performed including a site by dose interaction term in the main model.

These models will provide valid estimates and tests if any missing data is statistically ignorable (Laird, 1998). Dropout may be associated with reports of subjective withdrawal, and will be ignorable if available subjective scores prior to dropout are predictive of dropout. To assess possible effects of non-ignorability on inference, we will perform sensitivity analyses using pattern- mixture models and selection models. For pattern mixture models, subjects are grouped on the basis of their pattern of missing data. Usually, rarely occurring patterns are grouped, so as to keep the number of pattern-groups at a manageable level. This grouping defines a nominal variable, which is then used as a predictor in the analyses, although a covariate representing missingness on a continuous scale can also be used. The regression coefficients associated with this variable, and its interactions with the other predictors, quantify how response-predictor relationships differ across the different patterns of missingness. Overall predictor effects may be found by averaging over the patterns (Little, 1993). For longitudinal data, subjects are usually stratified according to the visit after which they dropped out. Hedeker and Gibbons (1997), and Hedeker and Rose (2000), apply these methods to mixed effects models in longitudinal data. Selection models (Little, 1995; Kenward, 1998; Verbeke and Molenberghs, 2000) take a different approach, by explicitly modeling the probability of drop out, and incorporating the predicted probabilities

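### The synopsis model for SOWS does not match the slope that 13.2 powers, 13.3.1 does not say which coefficient decides, and the primary model makes no use of the pre-dose reading as a common baseline

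*Combined protocol and SAP*

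**What the plan says.** - **9.2** defines the primary endpoint as "Reduction in subjective withdrawal as measured by the SOWS-Gossop". It names no time point, summary or contrast.
- **3.0, Statistical Methodology:** "Groups will be compared on 10 or more repeated SOWS responses during inpatient treatment". The fixed effects are given as "The SOWS total will be regressed on a three-level factor for site, and a two-level factor for pregabalin dose". No fixed time term and no interaction appear, although the covariance may have "a random slope included if necessary for fit". The contrast is said to be between pooled groups, yet the trial has two arms.
- **13.2** calls the slope the primary comparison: "comparing the groups on rate of decrease across days, using a linear group by time effect for the mixed effects models described above". It claims 80% power for a linear interaction of d = 0.44 SD, with 60 and 30 subjects, two-sided alpha 0.05, 40% dropout and within-subject correlation 0.5. The only model set out before 13.2 is the one in 3.0.
- **13.3.1:** "The groups will be compared on the 14 repeated SOWS-Gossop responses obtained during the seven-day detoxification period", with site, medication group and, in addition, "with time and group by time effects". It then says "Contrasts between the PGB group and the PGB-PLA group will be estimated from the model" without naming the contrast that decides.
- **9.1.2** puts the first Day 1 SOWS before the first dose and allows it to be repeated until the dosing criteria are met. **7.3.3.1** lets a missed 12:00 start move to 16:00.

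**The concern.** Three things are at stake.

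1. The synopsis and 13.2 describe different tests. A group term averaged over all readings and a group by time slope answer different questions and can disagree on the same data. If the analysis section does not name the deciding coefficient, the choice is open to challenge after unblinding.
2. The 80% depends on how the benefit develops. Section 13.2 says linear, but not at which reading d = 0.44 applies, how many readings are used or when the 40% drop out.
3. The first of the 14 readings is taken before any study drug. Under blinded random allocation the expected group difference there is zero, yet the model in 13.3.1 estimates one. That spends information the trial already collects.

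**Working it through.** **Inputs from the documents.** 60 and 30 subjects, two-sided 0.05, 40% dropout, correlation 0.5 and d = 0.44 SD (13.2); 14 readings (13.3.1); reading 1 pre-dose (9.1.2).

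**Assumptions.** Unit SD; compound symmetry; site left out; time t running evenly from 0 at reading 1 to 1 at reading 14. Three dropout timings were used: 40% gone by reading 14, 40% spread over 14 steps, and 40% spread over 7 daily steps.

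**Method.** The information matrix is the sum over arms and dropout patterns of n·p·X'V⁻¹X. It gives the SE of each coefficient and its expected value E under a given effect shape. Power = Φ(|E|/SE − 1.96), plus a negligible opposite tail.

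**Step 1: the plan's own figure.** The difference grows linearly from 0 to 0.44 SD at reading 14, and the slope model has a free group term.
- 40% gone by reading 14: SE 0.162; 0.44/0.162 = 2.71; Φ(0.75) = 77.5%. Detectable d = (1.96 + 0.84) × 0.162 = 0.454.
- 14 steps: SE 0.160, power 78.7%. 7 daily steps: SE 0.158, power 79.5%.

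The stated 80% at 0.44 is approximately reproduced. It needs about 14 readings: with 10, power is 66%.

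**Step 2: the synopsis model for the same effect.** The group coefficient has E = 0.179 and SE 0.1675, so 0.179/0.1675 = 1.07 and power is 18.7%. The other two timings give 19.3% and 19.7%.

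**Step 3: the slope test under other shapes, same 0.44 SD peak.** Each plateau rises evenly from reading 1 to the last reading of the named day and then holds. E is shown for 40% gone by reading 14; power covers the three timings except in the last row.

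| Shape | E | Power |
|---|---|---|
| Linear to Day 7 | 0.440 | 77-80% |
| Plateau by end of Day 2 | 0.327 | 52-53% |
| Plateau by end of Day 3 | 0.422 | 74-75% |
| Plateau by end of Day 4, 5 or 6 | 0.478, 0.497, 0.483 | 84-88% |
| Full benefit at first post-dose reading | 0.188 | 21% |
| Peak at Day 4, zero at the end (first two timings) | 0.054 | 6% |

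**Step 4: common mean at the pre-dose reading.** Removing the group term at reading 1 lowers the slope SE from 0.162 to 0.151 (40% gone by reading 14). Then 0.44/0.151 = 2.92 and Φ(0.96) = 83.1%. The other timings give 84.2% and 85.0%. Detectable d falls from 0.454 to 0.423. The results are the same whether the common time trend is linear or categorical.

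**Step 5: what else the constraint changes.** For non-linear shapes the expected coefficient moves as well.
- Day 2 plateau: E goes from 0.327 to 0.396 and power from 52% to 75%. The smaller SE alone would give 0.327/0.151 = 2.17, or 58%.
- Immediate benefit: E goes from 0.188 to 0.290 and power from 21% to 48%. The smaller SE alone would give 24%.

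Most of the gain for early-benefit shapes is therefore a change in what the coefficient measures.

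**Sensitivity.** With a random intercept of 0.5 plus AR(1) residuals at 0.5, a structure that 13.3.1 allows, power for the linear effect is 49% as planned and 59% with the common mean.

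**The case against.** The strongest reply is that the primary test is already named. Section 13.2 calls the linear group by time effect the primary comparison, and 13.3.1 fits a model that contains it. The synopsis may simply be abbreviated or out of date: its optional random slope presupposes a time variable, a contrast between pooled groups does not fit two arms, and 14 readings satisfy its lower limit of 10. This largely stands. The defect is a synopsis that conflicts with the body and an analysis section silent on the deciding coefficient.

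Five stronger readings are tempting, and the documents do not support them.
- **That the 80% is wrong.** It is reproduced to within about 3 points under a reasonable reading.
- **That the time course is unstated.** Section 13.2 says linear. What is missing is narrower: where d applies, the number of readings and the dropout timing.
- **That the plan leaves a categorical group by time test open.** No section proposes one; 13.2 says linear and the optional random slope points to continuous time.
- **That true power is 52-75% because pregabalin reaches steady state in 24 to 48 hours (7.2.4).** No section links plasma levels to the course of a SOWS difference, and the scheduled dose still rises on Day 2 (Table 3). The shapes in Step 3 are illustrations.
- **That the free group term biases the result.** The model in 13.3.1 is valid; the term costs precision only.

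The objection to the common baseline also stands in part: as Step 5 shows, under a non-linear course the constrained coefficient is no longer a pure rate-of-decrease contrast. The test remains valid under no effect, and the gain for the plan's own linear effect is real.

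**Conclusion.** The point holds as one of consistency and efficiency, and it should be fixed before unblinding. The synopsis model would have about 19-20% power for the effect on which the trial was sized, against 77-80% for the slope, so leaving the two descriptions side by side is not harmless. The 80% is sound for linear growth to 0.44 SD at the last reading. It does not carry over to an early plateau or a fading benefit, and it is somewhat exceeded if the plateau comes on Days 4-6. A common pre-dose mean adds about 5 to 6 points for the linear effect.

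The figures rest on compound symmetry at 0.5, the three dropout timings and assumed effect shapes. Absolute power is lower under serially correlated residuals, but the constraint still gained in the case tried.

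**What to change.** 1. **Align the text.** Give 3.0 the model of 13.3.1: 14 readings, time and group by time, and a contrast between the two arms. State in 13.3.1 that the linear group by time coefficient is the primary test.
2. **Use the pre-dose reading.** Constrain the groups to a common mean there and keep the common time trend flexible. Define the reading as the last SOWS before the first dose or, for subjects randomised but never dosed (13.6 analyses everyone randomised), the last Day 1 pre-dose SOWS available. The definition is needed because the reading can be repeated and a 16:00 start makes the 16:00 reading pre-dose too. Disclose that under a non-linear course the coefficient also picks up early level differences.
3. **Qualify the power statement.** Say in 13.2 that d = 0.44 is the difference at the last reading under linear growth. Report the average post-dose difference as a prespecified supportive contrast.

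The cost is wording and one model constraint, with no new data or visits. Making the average primary is a trade-off for the sponsor and not a correction. With a common baseline and 40% gone by reading 14, its power is 89% against 75% for the slope under a Day 2 plateau, but 46% against 83% under linear growth.
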